6.5 Data Management

Data will be submitted to the DCC via a distributed data entry system

DCC personnel will closely monitor clinical center adherence to study protocol and data collection practices to ensure complete and accurate research data. Monitoring will be performed via established data management procedures with on-site monitoring visits conducted at designated intervals or as needed to facilitate the smooth conduct of the study. At the time of the on-site visit, Data Coordinating Center personnel will have access to all study and patient documents as well as availability of clinical center personnel. All patient and study documents will be kept highly confidential.

Data Coordinating Center personnel meet weekly to discuss study status, recruitment, compliance, review data issues or interim analyses, clinical center participation, and other issues that arise during the course of the study.

7.0 Study Organization

7.1 Sites (See Table 1)

This study will be conducted at four clinical centers within the United States. The clinical centers are all tertiary care institutions and academic medical centers with extensive experience in the conduct of clinical trials of antiviral agents for the treatment of chronic hepatitis C. A Data

Coordinating Center will coordinate and oversee operations for the study, maintain the database and perform data analyses. This study will use the NIDDK repository. A central virology lab has yet to be selected.

7.2 NIH participants:

NIH participants will include project scientists and officials from NCCAM and NIDDK, as well as one or more consultants from NIDDK.

7.3 Committees:

A steering committee and an executive committee were formed to set policy and govern the conduct of the study.

Steering Committee: Serves as the primary governing body of the study; responsible for policy decisions; provides oversight in planning the overall study design, facilitates the conduct and monitoring of the study, and reporting study results; votes on and approves all major decisions, final protocol and subsequent amendments. Members consist of principal investigators of the clinical centers, the coordinating center, and the NCCAM and NIDDK project scientists. A chairperson is appointed by the NIH from among the clinical center PIs.

Executive Committee: Manages day-to-day issues of the study; makes decisions required between the Steering Committee meetings, as needed for efficient progress of the study, and reports its actions to the Steering Committee on a regular basis; organizes and sets agendas for Steering Committee meetings. Members consist of the Steering Committee chair, the Coordinating Center PI, and the NCCAM and NIDDK Project Scientists.

7.4 Subcommittees: Due to the small number of investigators and clinical sites involved in this study, all members will participate on ad hoc committees that will address issues that may arise during the course of the study including adherence, measurements, publications & presentations or ancillary studies. In addition, other subcommittees are as follows:

Coordinators Subcommittee: Attend to the day-to-day operations of the study including recruitment, protocol adherence, consistent and complete data collection at each clinical center. Make recommendations to the Steering Committee regarding any study issues that may require modification or resolution.

Exemption Subcommittee: Two hepatologists who are not recruiting participants into the study will review, on a case by case basis, protocol exemption petitions for subjects who do not meet one or more of the eligibility criteria (inclusion and exclusion) but are otherwise considered suitable candidates for enrollment. These exemptions will be considered only when they will not affect primary or secondary endpoints in the study. Examples might include liver biopsies or serological testing outside of predefined windows.

7.5 Data and Safety Monitoring Plan

Introduction

This phase II, randomized controlled trial aims to test the safety and efficacy of silymarin (Legalon[®]) in participants with chronic hepatitis C infection. The intervention poses greater than minimal risk to participants. Therefore, the data and safety monitoring plan (DSMP) for this study focuses on close monitoring by the principal investigators (PI) and prompt reporting of

excessive adverse events and all serious adverse events to the National Center for Complementary and Alternative Medicine (NCCAM), the National Institute of Diabetes and Digestive and Kidney Diseases (NIDDK), the Data and Safety Monitoring Board (DSMB) and to the participating centers' IRBs.

The Data Coordinating Center (DCC) will monitor clinical center performance (e.g., recruitment, retention, data completeness, timeliness of data collection and submission) and protocol compliance. These reports, with summaries of adverse event data, will be provided to the DSMB for their reports and calls or meetings, and to the Steering Committee at its annual meeting. DSMB reports will include both open and closed session reports, with only the latter including information by treatment arm.

Safety reports will be sent to the Principal Investigators and the NCCAM and NIDDK Project Officers. The Project Coordinator will be responsible for distributing these reports and assuring that all parties obtain copies of these reports.

The frequency of data review for this study differs according to the type of data and can be summarized in the following table:

Data type	Frequency of review
Recruitment	
Retention	
Protocol adherence(e.g., meeting	Quarterly reports for DSMB, NCCAM, and NIDDK
inclusion/exclusion criteria, treatment	
compliance)	
Adverse events	Quarterly reports for DSMB, NCCAM, and NIDDK
Serious Adverse Events (SAE)	Quarterly reports for DSMB, NCCAM, and NIDDK
Serious Adverse Events that meet	As they occur for DSMB, NCCAM, and NIDDK
expedited reporting criteria	
Laboratory data	Yearly

Data and Safety Monitoring Board

The DSMB members were appointed by the NCCAM and NIDDK. It consists of 5 members who have no financial, scientific, or other conflict of interest with the study. The DSMB acts as advisors to the NCCAM and NIDDK to monitor participant safety and study progress. The initial responsibility of the DSMB is to review the protocols and approve initiation of the study. Other responsibilities include reviewing informed consent documents; reviewing, commenting and approving the data and safety monitoring plan; assessing data quality, completeness, and timeliness; and evaluating recruitment and retention; monitoring risk versus benefit; consider factors external to the study when relevant information becomes available.

The DSMB will receive all MedWatch forms (FDA Form 3500A) submitted by the clinical centers for serious adverse events.

In the case of a serious adverse event requiring expedited reporting, the Data Coordinating Center will immediately notify NCCAM, the holder of the IND, the Project Scientists, and the DSMB. For the purposes of this study, reports of all deaths will be expedited, regardless of whether they are considered to be unexpected or related to study drug.

In accordance with IND safety reporting regulations, NCCAM, assisted by the Data Coordinating Center, will provide reports of serious adverse events requiring expedited reporting to the appropriate drug review division of the FDA and all participating investigators in writing within 15 calendar days of notification. Reports of serious, unexpected adverse events to the FDA will initially be conducted by telephone or fax within the required time frame (7 calendar days of notification by the clinical centers for telephone and fax safety reports). Following telephone/fax notification, written reports will be sent to the FDA.

The clinical centers are to report serious adverse events to the Data Coordinating Center within 24 hours of knowledge of the event so that notification can be provided as soon as possible following discovery of the event for reasons of patient safety. The clinical center PIs will be responsible for obtaining all information required to complete the adverse event report.

The DSMB will also review appropriate laboratory data annually.

Safety Monitoring

Adverse Events

The clinical centers will be instructed to collect information on all adverse events, defined as:

"Any unfavorable and unintended sign (including an abnormal laboratory finding, for example), symptom, or disease temporally associated with the use of a medicinal product, whether or not considered related to the medicinal product." (International Conference on Harmonisation of Technical Requirements for Registration of Pharmaceuticals for Human Use, *Guideline for Industry: Clinical SafetyData Management: Definitions and Standards for Expedited Reporting*, March 1995)

Adverse event information will be based on signs or symptoms obtained from the patient or family, during a physical examination, from results of laboratory testing, and clinical evaluation of the patient by the clinical center Principal Investigator (PI) and staff, and will include: the date and time of adverse event occurrence, severity, relation to medication administration, action taken, and outcome.

All serious adverse events, i.e., adverse events that result in, or are, any of the following:

- Death
- Life-threatening
- Inpatient hospitalization or prolongation of existing hospitalization
- Significant or permanent disability
- Congenital anomaly/birth defect
- Medical intervention to prevent permanent damage not requiring inpatient hospitalization
- Development of drug dependency or drug abuse

will be reported to the FDA and other entities (NCCAM, NIDDK, DSMB, IRBs) in cumulative fashion at designated time points (i.e., annual reports will be produced for the FDA and IRB; quarterly reports will be produced for the DSMB, NCCAM and NIDDK).

If the patient experiences a Serious Adverse Event:

1. Clinical center personnel will complete the FDA MedWatch form.

- 2. The completed MedWatch form must be faxed to the Coordinating Center at the University of Pittsburgh within 24 hours of knowledge of the event.
- 3. The Coordinating Center will immediately submit the MedWatch form to the chair of the DSMB if the SAE meets criteria for expedited reporting, and to the Project Scientists at NCCAM and NIDDK.
- 4. NCCAM, the holder of the IND, will report SAEs that meet criteria for expedited reporting to the FDA.

The Clinical Center Principal Investigators will be responsible for notifying their local Institutional Review Board.

Adverse Events Requiring Expedited Reporting

An adverse event will be subject to expedited reporting if it meets all of the following criteria, which are defined and discussed in detail below:

- 1) Serious in nature
- 2) Related to medicinal product
- 3) Unexpected

All deaths will be subject to expedited reporting, regardless of whether they are considered unexpected or related to medicinal product.

Related to Medicinal Product

The phrase "**related to the medicinal product**" implies causality or attributability to Legalon[®]. An adverse event should be considered to be related to Legalon[®] in situations in which a causal relationship cannot be ruled out. As noted above, the clinical center PIs will assess the degree of relatedness of the study medications and adverse events (i.e., unrelated, possibly related, probably related, definitely related).

Unexpected

The term **unexpected** refers to an adverse event that has not been previously observed or documented. A guideline is needed to define an adverse event as either expected or unexpected based on previous observation. The following documents or circumstances will be used to determine the expectedness of an adverse event:

- The Drug Label which contains the clinical and non-clinical data on therapy with Legalon[®].
- The natural history of chronic hepatitis C.
- Reports, which add significant information on specificity or severity of an otherwise known and documented adverse event, associated with the use of Legalon[®]. Thus more severe or more specific adverse events than had previously been observed are considered unexpected.

Expedited reporting is also required when there is an increased rate of occurrence of expected, serious adverse events related to the medicinal product. Hence, the DCC will prepare reports of rates of serious adverse events for review at DSMB calls and meetings.

Sufficient data on adverse events requiring expedited reporting must be obtained by clinical center personnel to enable clinical center personnel to complete the MedWatch form (FDA Form 3500A).

The DCC will send copies of the initial notification and written reports on adverse events to the NCCAM and NIDDK project scientists, the Chairperson of the DSMB, the other clinical centers,

and Rottapharm/Madaus. The Data Coordinating Center Principal Investigator, project coordinator, and data managers will be notified of serious adverse events.

All adverse event information will be included in the annual IND report to the FDA. The initial annual report will be within 60 days of the anniversary date that the IND went into effect. In addition, the Data Coordinating Center will provide the clinical centers with updated information on adverse events that occur throughout the study. This information may be used to change the protocol or consent form if necessary. The clinical centers will also need to provide this information to their respective IRB offices annually with their renewals, or in the timeframes required by their IRBs.

The data sections of the FDA IND annual report will be prepared by the DCC and sent to NCCAM. NCCAM will compile the final report, and then submit it to the FDA.

Stopping rules

There will be no planned interim analysis. Safety information will be examined by the DSMB quarterly.

Participant Confidentiality

The central database of the study is on a server at the Epidemiology Data Center (EDC) in the Graduate School of Public Health at the University of Pittsburgh secured behind locked doors and an alarm with password access provided only to authorized personnel. Backups are performed daily to guard against data loss due to an equipment or power failure. Scheduled backups and archives at the EDC protect central and local information from hard disk failures. Tape backup volumes and CD-ROM copies of critical project files are located in a secured offsite storage area to prevent data loss due to catastrophic events. Routine virus detection is also enforced for all EDC computers involved in the study. All critical information regarding database transactions is logged and stored in journal files. In the event of accidental corruption of the project database, a previous database state may be restored from backup volumes or journal files. All servers used for this project are connected to uninterrupted power supplies to protect equipment against electrical surges and outages. A secured, raised-floor computer room in an area with a burglar alarm houses all project server equipment.

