3.4.1 Dose Adjustment Guidelines

Specific dose adjustment guidelines are provided to investigators for adverse effects considered to be possibly related to silymarin, including laboratory abnormalities, adverse events, and vital signs changes. Investigators should utilize the "General Dose Reduction Guidelines" (Section 3.4.2) below. When practical, abnormal laboratory results should be confirmed as soon as possible following notification of the investigator. If appropriate, downward adjustments in one level increment (see below) should be considered.

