3.4.2 General Dose Reduction Guidelines

Dose reduction will be based upon severity ratings in accordance with the Common Toxicity Criteria for Adverse Events (CTCAE) (Appendix 4). Reporting of an abnormal ALT/AST results remains at the discretion of the clinical center Principal Investigator.

For grade 1, no dose reduction is needed. For grade 2 that persists over two consecutive safety visits and is not responsive to adjunctive symptomatic management, a level 1 dose decrease of study medication may occur at the discretion of the investigator. For grade 3 not responsive to adjunctive measures, a level 1 dose decrease of study medication is required. Subjects with grade 3 should be followed closely, possibly at more frequent intervals or via telephone contact to monitor in between regularly scheduled safety visits. If symptoms improve, return to previous dosing is allowed at the discretion of the investigator. For grade 4, treatment will be discontinued. It should be noted that certain toxicities carry different levels of significance for each patient and therefore, the investigator should use these as guidelines only, within the context of clinical judgment.

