Baseline	(Day	(0)) visit

Silymarin level	
HCV RNA	Serum 3ml (stored)
Sample storage	Fasting 10ml serum and 5ml plasma
Pregnancy Test	Urine, pre-dose
Adherence counseling	Use of MATI guidelines
Medication Education	Use of Medi-dose cups and patient diaries that record doses taken and alcohol use
Study Medication Administration	Supervised by research coordinator
Questionnaires	SF-36, CLDQ, CES-D, ASE

4.3 Treatment Period: Silymarin and/or placebo will be administered as a total of 5 capsules administered three times daily. Treatment will be continued for 24 weeks. During the treatment period, participants will return for safety and efficacy evaluations at treatment weeks 2, 4, 8, 12, 20, 24 (end of treatment). Phone calls will be made to the participants at weeks 6 and 16 to monitor safety, compliance with study medication and concurrent medications. There is an acceptable window of +/- 3 days for all visits. The following procedures will be performed at the study visits:

Vital signs and weight at each visit; physical exam every 3 months or
as needed
Each visit
Each visit
Each visit
Each visit; ALT, AST, AlkPO4, total bilirubin, albumin, BUN, creatinine,
glucose.
Week 12 and 24 only: fasting triglycerides, glucose, insulin
Urine, each visit
Week 24
Week 24
Weeks 2, 4, 12, 24
Weeks 12, 24 (3 ml serum, stored)
Week 12
Fasting 5ml serum and 3ml plasma at weeks 12 and 24 only
Each visit according to assigned schedule or random sample
each visit
Weeks 4, 12, 24: SF-36, CLDQ, CES-D, ASE
Each visit

Table 5Safety and Efficacy Visits

Monitoring and	Monitoring by dose counts and review of diary entries
Counseling	

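### By-arm review of ALT/AST worsening is assured only once a year in a 24-week trial, because laboratory data go to the DSMB yearly and reporting of abnormal ALT/AST is left to each site

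*Protocol*

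**What the plan says.** Section 7.5 sets review frequencies in a table introduced by "The frequency of data review for this study differs according to the type of data". Adverse events and serious adverse events go to the DSMB in quarterly reports, and serious events that meet the expedited criteria go as they occur. The laboratory row reads yearly. The DSMB paragraph repeats this: "The DSMB will also review appropriate laboratory data annually". The stopping-rules paragraph reads: "There will be no planned interim analysis. Safety information will be examined by the DSMB quarterly". On who sees results by arm, section 7.5 says: "DSMB reports will include both open and closed session reports, with only the latter including information by treatment arm".

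The adverse event definition quoted in section 7.5 covers abnormal laboratory findings, and centers are told to collect all adverse events. Section 3.4.2 carves out one case: "Reporting of an abnormal ALT/AST results remains at the discretion of the clinical center Principal Investigator".

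The values themselves are collected often. The treatment-visit table in section 4.3 lists chemistry as "Each visit; ALT, AST, AlkPO4, total bilirubin, albumin, BUN, creatinine", and the same section fixes the exposure: "Treatment will be continued for 24 weeks". Section 3.4.1 bases dose adjustment on "adverse effects considered to be possibly related to silymarin, including laboratory abnormalities, adverse events, and vital signs changes", and section 3.4.4 lists laboratory tests as a safety measurement.

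**The concern.** Safety is the first primary objective. The participants have chronic hepatitis C and the drug is given for its effect on the liver, so worsening liver enzymes are a natural safety signal to follow. Site investigators see each participant's values but are masked, so none of them can tell whether rises cluster in one silymarin arm. Only the DSMB, through the closed report, can make that comparison.

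The DSMB can learn of a non-serious ALT/AST rise in two ways. One is the quarterly adverse event report, which contains the rise only if the site chose to report it. The other is the laboratory review, which comes once a year. With no common threshold, the four centers may report at four different levels, so the quarterly ALT/AST counts are not a dependable basis for comparing arms. The assured route has an interval more than twice the treatment period. A difference between arms could be seen first when many of those affected have already stopped the drug.

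**Working it through.** **Inputs.** Laboratory review interval: 52 weeks (section 7.5, table and DSMB paragraph). Adverse event review interval: quarterly, 13 weeks (section 7.5). Treatment: 24 weeks; follow-up: a further 12, giving 36 weeks in all (section 3.4). Participants: 153, 51 per arm (section 6.3). The protocol gives neither the accrual rate nor the date of the first annual review. Both are assumptions below.

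**Interval against exposure.** 52/24 = 2.17 times the treatment period, and 52/36 = 1.44 times total participation. This comparison needs no assumption.

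**Share with no review during treatment.** With entry spread evenly relative to the review dates, the share is max(0, 1 − 24/interval).
- Yearly: 1 − 24/52 = 0.54, or about 0.54 × 153 ≈ 82 participants.
- Quarterly: 24 exceeds 13, so 0. Every participant who completes treatment has at least one review during it.
- For the full 36 weeks under yearly review: 1 − 36/52 = 0.31.

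**Mean wait from a laboratory result to the next review**, interval/2: 26 weeks for yearly, 6.5 weeks for quarterly.

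**Chance that the next review falls after that participant's treatment has ended**, for a change at a random time in the 24 weeks. On average 12 weeks of treatment remain.
- Yearly: 1 − 12/52 = 0.77.
- Quarterly: 6.5/24 = 0.27.

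**Sensitivity to the even-entry assumption.** Suppose instead steady accrual of 1, 2, 3 or 4 per arm per month, with the first annual review 3, 6, 9 or 12 months after the first dose. Participant i (0 to 50) starts at month i/rate and is treated for 5.52 months. Across the 16 combinations, between 21 and 34 of 51 per arm (41% to 67%) have no laboratory review during treatment. The extremes both occur at 3 per month: 21 with the first review at month 6, and 34 with it at month 12.

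**Which results this applies to.** The figures describe the laboratory review route only. Under the text:
- Serious ALT/AST events: reported as serious adverse events, quarterly or expedited.
- Non-serious abnormalities other than ALT/AST: adverse events by definition, so quarterly.
- Non-serious ALT/AST rises that a site reports: quarterly.
- Non-serious ALT/AST rises that a site does not report: yearly.

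Only the last group depends on the yearly cycle. The protocol gives nothing from which its size could be derived.

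**The case against.** The best case against the point is that the cadence is a deliberate, coherent choice. The section 7.5 table says frequencies differ by data type, and the annual laboratory review adds to the quarterly event flow. The DSMB itself reviews and approves the monitoring plan. Individual protection is not annual: chemistry is measured at every treatment visit, grade 3 events that do not respond to other measures call for a dose decrease, grade 4 events lead to discontinuation, and an investigator may request unmasking for an event judged drug-related. Phase I, as summarized under dose selection in section 1.0, showed 5 mild-to-moderate events in 4 of 30 Legalon patients and none above 840 mg/day. Everyone enters with ALT of at least 65 IU/L, so nearly every early value is abnormal and some discretion is sensible. More frequent by-arm ALT tables also give the DSMB more looks at the efficacy variable.

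Much of this stands, and it rules out several stronger readings:
- A reader might infer that section 7.5 contradicts itself. It does not: quarterly review of safety information is compatible with a table that sets laboratory data apart.
- A reader might infer that all laboratory abnormalities wait a year. They do not, because the adverse event route covers them; the discretion in section 3.4.2 is confined to ALT/AST.
- A reader might take the 54% as a measure of harm. It is calendar arithmetic, and no hepatotoxicity signal appears in the protocol.
- A reader might link this to the remarks in sections 6.1 and 6.3 that toxicity stopping rules are set aside in the power calculations. Those remarks change no result.

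What the objection does not answer is the between-arm comparison. Visit-level monitoring by masked investigators cannot supply it, and unmasking one participant does not either. High entry ALT justifies discretion over values that are merely abnormal. It does not justify having no level of worsening at which reporting is required.

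**Conclusion.** The point holds in a narrow form. Yearly laboratory review is stated twice and exceeds the treatment period by a factor of 2.17. For ALT/AST the quarterly adverse event route depends on site discretion with no floor. A between-arm excess of non-serious ALT/AST rises is therefore assured of unmasked review only once a year. About 54% of participants complete treatment without such a review during it if entry is even, or 41% to 67% per arm over the accrual and review dates assumed above; under quarterly review it is 0%. These figures rest on assumed entry and review dates and say nothing about how many rises would go unreported.

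This is a minor weakness in oversight. It does not bear on the validity of the efficacy analysis, and individual participants are still monitored at each visit.

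**What to change.** 1. In the section 7.5 table and the DSMB paragraph, change laboratory data from yearly to quarterly. Present them by arm, placebo included, in the closed report as counts of participants whose ALT/AST or bilirubin has worsened from baseline. Show no response rates and run no test.
2. In section 3.4.2, set one clinically chosen ALT/AST level relative to the participant's own baseline (for example 2 times) at which adverse event reporting is required. Keep investigator discretion below it. The multiple is only an illustration; the protocol does not supply one.

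No numerical stopping boundary is proposed, and the DSMB's advisory role to the funding institutes stays as it is.

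The cost is one table cell, one sentence in the DSMB paragraph and one in section 3.4.2. The values are already collected at each treatment visit, and DSMB reports already go out quarterly with a by-arm closed part. Sites will file somewhat more ALT/AST reports. The DSMB will see worsening more often in a variable that is also the efficacy measure; limiting the table to worsening, with no test, keeps that exposure small and spends no alpha. Sample size and power do not change.
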